### **4.3 Subject Confidentiality**

Enrolled Subjects will be assigned a unique, pseudo-anonymous identifier that will be used to maintain confidentiality of each subject's medical information. Subject names will not be captured on the CRFs. All subject identifiers except the unique pseudo-anonymous identifier should be redacted from any images or other data submitted from the participating site to the Sponsor or the Sponsor's designated reviewers for analysis. All information concerning subjects or their participation in this study will be considered confidential. Only the authorized Sponsor, designated representative personnel, designated consultants and regulatory agencies will have access to these confidential files.

### **4.4 Sample Size Summary**

A maximum of 900 subjects may be enrolled in this study.

**Roll-In Subjects:** Up to 105 subjects (the first 1 to 3 Enrolled Subjects at each site) will be treated with the FARAPULSE devices in a manner consistent with the randomized Pulsed Field Group and will be analyzed and reported separately.

**ITT Subjects:** An estimated 450 MITT Subjects will be required to support the proposed non-inferiority outcomes. Interim sample size re-estimation may decrease this number to 350 or increase it to a maximum of 750. Up to 45 additional subjects (6%) may be enrolled to compensate for those ITT Subjects who do not meet the criteria for the MITT Population.

#### **4.5 Investigational Sites**

The clinical study will be conducted at up to 35 qualified investigational sites in the United States. No site may enroll more than 45 ITT Subjects (excludes Roll-In Subjects and ITT Subjects who do not qualify for the MITT population) with an intended minimum of 10 subjects per site. Should interim sample size re-estimation lead to an increase in the number of MITT Subjects greater than 450, each site will be limited to 10% of the increased total.

#### **4.6 Duration of Study and Subject Participation**

Study start-up, inclusive of site initiation and Investigator training, is estimated to take 6 months. The enrollment period for the first 600 subjects (105 Roll-Ins plus 495 ITT Subjects) is estimated to take 18 months and subjects will be followed for up to 13 months. There will be a 3-month period of site close-out visits, for a planned study duration of approximately 40 months. Coronavirus Disease 2019 (COVID-19)-related disruptions and interim sample size re-estimation may alter this timeframe.

Subject participation is anticipated to be  $13 \pm 1$  months to allow for screening, pre-procedural diagnostic procedures, randomization, treatment and  $12 \pm 1$  months of study follow-up. If a subject requires a Rescheduled Index Procedure, this may prolong participation by up to 2 to 3 months.

#### **4.7 Schedule of Events and Assessments**

Subjects will complete the following visits and assessments as indicated below and as summarized in **Table 3**, (ITT Subjects) and **Table 4**, (Roll-In Subjects).

Assessments that are stipulated as remote may also be performed in-person at the investigational site at the Investigator's discretion with subject agreement.

All protocol-stipulated assessments below will be entered into the appropriate CRFs.

Assessments are to be performed within the specified assessment windows.

When COVID-19-related disruptions (**Section 6.3.8**) interfere with the performance of protocol-stipulated follow-up assessments, study sites and Sponsor personnel will adjust procedures to optimize data acquisition while protecting the health, safety and welfare of all study participants. Study subjects, sites, IRBs and the FDA will be informed of COVID-19-related changes in the study.

This protocol does not specify how remote assessments should be performed, but these will be specified in related study documentation and may be modified as necessary during the conduct of the study. The method(s) used during the course of this study to interact with study participants and to acquire data remotely will be consistent with relevant FDA Guidance Documents and will be reported in the Clinical Study Report.

#### **4.7.1 Baseline Assessment**

Type of Assessment: In-person at investigational site
--

The completion of the Baseline Assessment requires an in-person visit. Such assessments must be deferred if this is not possible.
--

The below baseline data will be generated in the window beginning 30 days prior to the Consent Date and ending on the date of the Index Procedure, unless otherwise specified. This data will include:

- Demographics including gender, height and weight
- Pertinent medical and cardiovascular history
- AAD and anticoagulation medication history
- Cardiac physical examination
- Pregnancy test (all women of child-bearing potential)
- Hematocrit, hemoglobin, electrolytes, blood urea nitrogen (BUN), creatinine
- COVID-19 testing by site
  - PCR for SARS-CoV-2 virus or equivalent testing, or
  - Confirmation of successful vaccination with an FDA-approved vaccine
- 12-lead ECG. ECGs with any arrhythmia will include a rhythm strip for ACL submission.
- Imaging (within the window beginning 90 days prior to the Consent Date and ending on the date of the Index Procedure)
  - TTE
  - Cardiac CT or MRI establishing PV dimensions
- NYHA Classification
- National Institutes of Health Stroke Scale (NIHSS) score by NIHSS-certified site personnel
- CHA2DS2-VASc score
- AF symptom assessment
- Quality of Life Measures:
  - The EuroQol standardized questionnaire of health states (EQ-5D-3 L)
  - The Atrial Fibrillation Effect on QualiTy-of-Life Questionnaire (AFEQT) quality of life assessments

**Introduction to the EM / Holter Device:** At the Baseline Assessment, the subject will receive an introduction to EMs, Holters, the hardware and how it will be utilized during the follow-up period. The importance of compliance with these critical assessments will be stressed.

#### **4.7.2 Index Procedure / Rescheduled Index Procedure**

Type of Assessment: In-person at investigational site
--

The performance of the Index Procedure / Rescheduled Index Procedure and the Pre-Discharge Assessment both require an in-person visit. The Index Procedure / Rescheduled Index Procedure must be deferred if this is not possible.
---

The Index Procedure will be performed according to **Section 5.2**. Procedural data will be collected including:

- Transesophageal echocardiography (TEE) or intracardiac echocardiography (ICE) will be utilized prior to transseptal puncture for exclusion of LA thrombus.
- Pregnancy test (all women of childbearing potential if baseline pregnancy test obtained more than 30 days prior to procedure)
- Post-ablation 3D electroanatomical maps (at Investigator discretion)
- Post-ablation fluoroscopic examination of diaphragm motion to assess phrenic nerve response
- Adverse events
- Procedural times
- Lesion set data
- Peri-procedural anticoagulation data:
  - For subjects on a novel oral anticoagulant (NOAC) whether NOAC therapy was interrupted for procedure
  - For subjects on warfarin, a pre-treatment international normalized ratio (INR) value
  - Heparin administration and timing
- Device deficiencies and malfunctions
- For Thermal Subjects:
  - The specific thermal technology used, including manufacturer/model
  - The use of any esophageal monitoring, cooling or manipulation during the ablation procedure

#### **4.7.3 Pre-Discharge Assessment**

Type of Assessment: In-person at investigational site
--

Prior to hospital discharge study data will be collected including:

- Adverse events
- Hematocrit, hemoglobin, electrolytes, BUN, creatinine
- Data regarding the use, changes in or discontinuation of anticoagulation, rate control and/or antiarrhythmic medications.
- Cardiac rhythm as determined by a 12-lead ECG. ECGs with any arrhythmia will include a rhythm strip for ACL submission.
- Occurrence, date, indication and outcome of any cardioversion(s)
- Assessment of subject blinding

[figure not shown]
**EM Training:** The subject will be reminded regarding the use of the EM hardware, the importance of event monitoring and of the importance of the Day 60 EM Training.

**Pre-Discharge Stroke Evaluation for non-Neurologic Assessment Subjects:**

- NIHSS score by NIHSS-certified site personnel
- If either of the following occurs:
  - The post-procedure NIHSS score has increased by 1 or more points over the pre-procedure NIHSS score OR
  - There is a clinical suspicion of stroke or TIA

Then a consulting neurologist will perform a stroke assessment and include the results of a concurrent brain MRI. This assessment will be sufficient to determine with reasonable certainty whether a stroke, TIA or neither have occurred, using the definitions in **Table 5**. If a stroke is diagnosed the subject will be assessed using a Modified Rankin Scale. Please refer to **Figure 6**.

**Figure 6 Pre-Discharge Stroke Evaluation, Non-NAS Subjects**

[figure not shown]

**Pre-Discharge Stroke Evaluation for Neurologic Assessment Subjects:**

- A post-procedure brain MRI as specified in **Section 5.8**.
- NIHSS score by NIHSS-certified site personnel
- If any of the following occurs:
  - The brain MRI is positive for SCE or SCL findings
  - The post-procedure NIHSS score has increased by 1 or more points over the pre-procedure NIHSS score OR
  - There is a clinical suspicion of stroke or TIA

Then a consulting neurologist will perform a stroke assessment and review the NAS-stipulated brain MRI. This assessment will be sufficient to determine with reasonable certainty whether a stroke, TIA or neither have occurred, using the definitions in **Table 5**. If a stroke is diagnosed the subject will be assessed using a Modified Rankin Scale. Please refer to **Figure 7**.

**Figure 7 Pre-Discharge Stroke Evaluation, NAS Subjects**

#### **4.7.4 Day 7 Assessment**

Type of Assessment: Remote
Window: Days 7 – 11
The Day 7 Assessment is essential to establish the primary safety endpoint and every effort must be made to complete this assessment between Day 7 and Day 11.
If the assessment is delayed, the onset date of an AE must be elicited as carefully as possible to establish whether it occurred within the interval between the ablation procedure and Day 7, or thereafter.

Subjects will be assessed remotely between Day 7 and 11 post-Index Procedure / Rescheduled Index Procedure. Study data will be collected by interview, including:

- Adverse events
- Data regarding the use, changes in or discontinuation of anticoagulation, rate control and/or antiarrhythmic medications.
- Recurrent arrhythmia, cardioversions, ablations or hospital admissions since discharge
- The date, time and communication method(s) used to collect the data remotely

#### **4.7.5 Day 30 Assessment**

Type of Assessment: Remote
Window: 30 ± 7 Days

Discharged subjects will be assessed remotely 30 days ( $\pm$  7 days) post-Index Procedure / Rescheduled Index Procedure. (Any subject who continues to be hospitalized 30 days post-ablation will have their 30-Day Visit assessment performed in-hospital). Study data will be collected by interview including:

- Adverse events
- Data regarding the use, changes in or discontinuation of anticoagulation, rate control and/or antiarrhythmic medications.
- Recurrent arrhythmia, cardioversions, ablations or hospital admissions since 7-day telephonic assessment
- The date, time and communication method(s) used to collect the data remotely

#### **4.7.6 Day 60 EM Training and AAD Discontinuation**

Type of Interaction: Remote
Window: 60 ± 10 Days

**EM Training:** At Day  $60 \pm 10$  days following the Index Procedure / Rescheduled Index Procedure, the subject will receive an EM and receive remote training regarding its use and the importance of event monitoring. The subject will be instructed to begin

using the EM at the time of the Day 90 Assessment and weekly thereafter and also for any symptomatic episodes throughout the remainder of study follow-up.

**AAD Treatment:** During this same subject interaction, Class I / III AADs should be stopped – if they have not already been discontinued – to allow assessment of off-drug freedom from recurrent AF, AFL or AT (the primary effectiveness endpoint). See **Section 5.9.**

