#### **4.7.7 Day 90 Assessment**

**Type of Assessment: In-person at investigational site required; remote only for documented COVID-19 related disruption.**

**Window:  $90 \pm 14$  Days**

**If a COVID-19-related disruption prevents an in-person visit within the visit window:**

- As much data as possible may be collected remotely.
- A cardiac MRI or CT scan performed at another healthcare site may be utilized, preferably with the same modality as the baseline scan, or the imaging procedure may be delayed for up to 3 months.
- If a fluoroscopic examination is required due to prior diminished phrenic nerve response, an inspiration/expiration chest X-ray (CXR) performed in-person or at another healthcare site may be substituted.

Subjects will be assessed at Day  $90 \pm 14$  days following the Index Procedure / Rescheduled Index Procedure.

**EM Review:** During this assessment, the subject will be queried as to their understanding and use of the EM. Remedial training will be supplied as required.

The subject will be instructed to begin weekly scheduled and symptomatic use of the EM and the critical importance of full compliance for study success will be stressed.

Study data will be collected at the 90-Day Visit including:

- Adverse events
- Data regarding the use, changes in or discontinuation of anticoagulation, rate control and/or antiarrhythmic medications
- Recurrent arrhythmia, cardioversions, ablations or hospital admissions since last visit
- Radiologic examination of the diaphragm (fluoroscopic sniff test or inspiration/expiration CXR) if the post-Index / Rescheduled Index Procedure fluoroscopy indicated diminished phrenic nerve response and resolution has not been previously demonstrated
- Cardiac rhythm as determined by a 12-lead ECG at the time of the visit (in-person assessment only). ECGs with any arrhythmia will include a rhythm strip for ACL submission.
- Cardiac CT or MRI scan of the same type as the baseline scan to assess the dimensions of the PVs. For subjects with a CICL-confirmed 70% or greater PV

diameter reduction, a Month 12 follow-up Cardiac CT or MRI scan of the same type as baseline will be scheduled to assess PV dimensions.

- Follow-up brain MRI as specified in **Section 5.8.2** (only for NAS Subjects with a confirmed post-procedural SCE or SCL on the post-procedural brain MRI)
- For any subject diagnosed with stroke during the Pre-Discharge Assessment, a Modified Rankin Scale assessment.

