## 4.8 Schedule of Events

**Table 3 Schedule of Events – ITT Subjects**

Assessment	Baseline  (In-person)	Index Procedure (In-person)	Pre- Discharge (In-person)	Day 7 (7-11 days) (Remote  )	Day 30 (± 7 days) (Remote  )	Day 60 (± 10 days) (Remote  )	Re- Ablation Procedures (In-person)	Day 90 (90 ± 14 days) (In-person)	Month 6 (180 ± 30 days) (Remote  )	Month 12 (360 ± 30 days) (In-person)	Unscheduled (In-person/ Remote  )
Informed consent, baseline assessments	X 										
AAD and anticoagulant medications	X		X	X	X	D/C AADs	X	X	X	X	X
Recurrent arrhythmia, cardioversions, ablations, hospital admissions			X	X	X		X	X	X	X	X
Pregnancy test	X 	X 					X 				
COVID-19 testing by site	X										
12-lead ECG	X		X					X		X	X
HCT, HGB, electrolytes, BUN, creatinine	X		X								
Transthoracic echocardiogram (TTE)	X										
Event monitors	Training		Training			Training		Weekly + symptomatic transmissions			X
72-Hour continuous ECG (Holter)	Training		Training						X	X	
Cardiac CT/MRI for PV dimensions	X						X 	X			X 
TEE/ICE to exclude LA thrombus		X 					X 				
NIHSS	X		X								
Radiologic examination of diaphragm		X					X	X 			X 
AF Symptom Assessment	X										X
EQ-5D-3 L & AFEQT assessments	X										X
Non-NAS subjects: Neuro assessment			X 					X 			
NAS subjects: Neuro assessment			X 					X 			
Assessment of subject blinding			X							X	
Adverse events		X	X	X	X		X	X	X	X	X

 All Baseline Assessments must be generated in the window beginning 30 days (90 days for TTE and cardiac CT/MRI) prior to the Consent Date and ending on the date of the Index Procedure.

 Assessments that are defined as remote may also be performed at the investigational site (non-remote) at Investigator discretion and subject agreement.

 Baseline assessments include the inclusion/exclusion criteria and the data stipulated in **Section 4.7.1**.

 Females of childbearing potential only. The pre-procedural pregnancy test is not required if the Index Procedure / Rescheduled Index Procedure is within 30 days of the baseline pregnancy test.

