## 5.5 Start Date, Blanking Period and Index Procedures

The day of the Index Procedure or Rescheduled Index Procedure is the Start Date (Day 0) for follow-up scheduling. The Blanking Period consists of a subject's Day 0 through and including Day 90. During the Blanking Period, any occurrence of Detectable AF, AFL or AT will be documented; however, occurrences of AF, AFL or AT during this time will not be considered Treatment Failures.

[figure not shown]
For subjects who undergo ablation at the Index Procedure, the follow-up intervals for safety and effectiveness are depicted in **Figure 9** below:

**Figure 9** Index Procedure Blanking and Follow-Up Intervals

For subjects who undergo ablation at a Rescheduled Index Procedure the follow-up intervals for safety and effectiveness are depicted in **Figure 10** below. The follow-up intervals for effectiveness and safety are still based on the day of the ablation procedure (Day 0). Pre-ablation AEs that occur between the Index Procedure and the day before the Rescheduled Index Procedure will not be included in the safety analyses, but will be documented and reported separately, with the day of occurrence being enumerated from the day of the Index Procedure that was deferred.

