### **6.3.11 Detectable AF, AFL or AT**

Detectable AF, AFL or AT is an episode of AF, AFL or AT which:

- Is permanently recorded for review
- Contains at least 30 seconds of continuous interpretable signal
  - Exception: Continuous AF, AFL or AT for the entirety of a 12 lead ECG constitutes Detectable AF, AFL or AT if the continuous interpretable signal is 10 seconds or longer
- Includes symptomatic and asymptomatic episodes.
- Excludes CTI isthmus-dependent AFL when the mechanism is confirmed electrophysiologically.

Such episodes are not AEs under this protocol unless deemed to be caused by an ablation procedure.

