#### 10.1.2 Event Monitors

Each subject:

- Will be introduced to the use and importance of EMs at the Baseline visit
- Will be fully instructed on the use of an EM at the Day 60 EM training.

Either the ACL or the site will provide the subject with an EM not later than the Day 60 EM training to be used beginning at the time of the Day 90 Assessment and weekly thereafter and also for any symptomatic episodes throughout the remainder of the 12-month study follow-up.

Careful monitoring and subject follow-up will be implemented to ensure compliance with the required weekly scheduled and ad hoc symptomatic utilization and transmission of the EMs. Individual missed weekly transmissions will not be counted as protocol deviations, but a subject with less than 80% of weeks covered by at least one transmission at the end of follow-up will be considered a protocol deviation.

The EM will be returned to the ACL or the site at the time of the subject's exit from the study. ECG data from the EM will be analyzed by the ACL.

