The piecewise exponential model has a hazard function that is piecewise constant (or “flat”). With a fine enough partition, a piecewise exponential model can be used to approximate any hazard function⁹. However, to produce stable estimates of hazard parameters, a reasonable number of events must be observed in each “piece” of the partition, so too fine a partition is impractical. The partition (0–90, 90–104, 104–150, 150–210, 210–360 days) is justified primarily by evidence observed in the Fire and Ice trial³, where the time to primary event is depicted in **Figure 2** (from reference 3), in which it is observed that the shapes of the curves appear to change at approximately 90 days (the end of the blanking period), two weeks later (104 days), and around the 6-month visit window (starting at 180 – 30 = 150 days and ending at 180 + 30 = 210 days). From 210 to 360 days, the curve rises at a reasonably constant exponential rate. A similar assessment of the time-to-event curves from other trials^{14,16,17,18} indicates that, although this partition of the time axis may be finer than necessary, it can also appropriately model their respective hazards.

Censoring Procedures

The model in part B, above, is based on censoring or event times up through post-blanking day Day 360. Subjects without a known event will be considered censored at the later of their last Event Monitor or last Holter Monitor. Since the 12-month follow-up window extends to Follow-up Day 390, all events and censoring times > 360 days will be assigned a time of 360 Days when fitting the piecewise exponential models.

Predictive Probabilities and Posterior Inference

At every analysis, the imputations described above are executed $M=5000$ times, resulting in M completed datasets, filled with only E or N final outcome values. With the $\text{Beta}(0.5, 0.5)$ prior distributions specified in Section 9.1, each of the M completed datasets implies a conjugate Beta posterior distribution for both P_T and P_C . From these, the posterior probability $\text{Pr}(P_T > P_C - 0.15 | m^{\text{th}}$ completed dataset) is computed. This is used in the following ways:

- At each sample size look: The proportion of these M completed datasets that result in $\text{Pr}(P_T > P_C - 0.15 | m^{\text{th}}$ completed dataset) $> \Psi_{\text{eff}}$ is the predictive probability of future success for the effectiveness objective. As described in Section 12, this is used to determine whether to curtail enrollment.

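### Event monitoring starts at the Day 90 visit, not when blanking ends, so a subject seen late in the visit window can have up to 13 post-blanking days without it

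*Protocol*

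**What the plan says.** Protocol 5.5 fixes the end of blanking by study day: "The Blanking Period consists of a subject's Day 0 through and including Day 90". Under 7.4, a recurrence counts as a failure after that.

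The start of event monitor (EM) use is fixed by a visit. Section 4.7.6 has the subject begin "using the EM at the time of the Day 90 Assessment and weekly thereafter". Section 4.7.7 says of that visit, whose window is 90 ± 14 days: "The subject will be instructed to begin weekly scheduled and symptomatic use of the EM". That wording covers symptomatic as well as scheduled use. Section 10.1.2 repeats that the device is "to be used beginning at the time of the Day 90 Assessment and weekly thereafter". The same section shows that the device arrives well before: "Either the ACL or the site will provide the subject with an EM not later than the Day 60 EM training". No section gives a study day for the first transmission.

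A Detectable AF, AFL or AT episode must meet several conditions in 6.3.11, among them "Is permanently recorded for review". The recording need not come from the EM.

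On the analysis side, SAP 13.1 treats a subject who is event-free at the 12-month assessment as a known non-event. It censors subjects without an event at the later of their last EM or last Holter. It has no rule for a stretch without monitoring at the start.

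**The concern.** The endpoint clock and the main detection tool start on different days. A subject seen on Day 80 is monitored from the first post-blanking day. One seen on Day 104 starts 13 full days late, and a symptomatic episode on Day 95 would occur with the device at home but not yet in authorised use. If nothing else captures that subject's arrhythmia, the analysis records a success.

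The direction matters more than the size. Undetected failures raise the apparent success rate in both arms, but by more in the arm with more failures. A real deficit therefore looks smaller, which makes non-inferiority easier to declare. SAP 15.4 and 15.5 simulate administrative censoring and dropout, not a gap at the start of monitoring, so the type I error tables do not cover this.

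**Working it through.** **Inputs.** Blanking to Day 90 (Protocol 5.5). Visit window Day 76 to 104 (4.7.7). Piecewise hazards for Eff1, Eff2 and Eff3 (SAP 15.2). Margin 0.15, Beta(0.5, 0.5) priors and threshold 0.956 (SAP 9.1). Null of 50% v 65% (SAP 14). The documents give neither the distribution of visit days nor the chance that a missed recurrence is caught later. Both are assumptions here.

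**Step 1: reproduce the SAP's values.** With S(t) = exp(−H(t)) under Eff1, H(90) = 90 × 0.00011167 = 0.01005, so S(90) = 0.990. H(104) = 0.01005 + 14 × 0.002197976 = 0.04082, so S(104) = 0.960. Both match SAP 15.2, as do the stated values for Eff2 and Eff3.

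**Step 2: scale to the wanted success rate.** As in the SAP, multiply the hazards by k = ln(target) / ln(S(360)). For Eff1, k is 1 at 65% and 0.6931/0.4308 = 1.609 at 50%. For Eff2, with S(360) = 0.686, k = 0.4308/0.3769 = 1.143 at 65%.

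**Step 3: first failures in the two weeks after blanking.** The proportion is S(90) − S(104). For visits spread evenly over the window, average S(90) − S(max(v, 90)) over visit day v from 76 to 104.

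| Method | Day 90–104, 65% arm | Day 90–104, 50% arm | Before own visit, 65% arm | Before own visit, 50% arm |
|---|---|---|---|---|
| Eff1 (default) | 3.0% | 4.8% | 0.75% | 1.2% |
| Eff2 | 11.5% | 17.7% | 3.55% | 5.5% |
| Eff3 | 9.9% | 15.0% | 2.5% | 3.9% |

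The interval includes Day 104, the day monitoring would begin, so it slightly overstates a 13-day gap. Using Day 103 under Eff1, S(103) = exp(−(0.01005 + 13 × 0.002197976)) = 0.962, and the figure is 2.8%.

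**Step 4: effect on the non-inferiority test.** If a fraction q of gap failures is never detected later, observed success = true success + q × gap proportion. For Eff1, even visits and q = 0.5:

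- Pulsed Field: 0.50 + 0.5 × 0.0120 = 0.506
- Thermal: 0.65 + 0.5 × 0.0075 = 0.654
- Observed difference: −0.148 instead of −0.15

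The probability of declaring non-inferiority comes from exact binomial enumeration at a fixed 225 per arm. With full detection it is 4.7%, close to the 0.0487 in SAP Table 4 for the adaptive design.

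| Even visits, share never detected later | Eff1 | Eff2 | Eff3 |
|---|---|---|---|
| 10% | 4.8% | 5.2% | 5.0% |
| 25% | 5.0% | 5.9% | 5.5% |
| 50% | 5.2% | 7.2% | 6.3% |

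As an extreme, if every visit fell on Day 104 and half of gap failures were never detected, Eff1 gives 6.9%.

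**The case against.** The strongest reply is that only the EM is missing, not all detection. A 12-lead ECG is taken at the in-person Day 90 visit and is required at unscheduled on-site visits (4.7.7, 4.7.11). Any other permanent recording can qualify. Cardioversion, Class I/III drug use and re-ablation are failures in their own right under 7.4, and the Day 90 visit asks about them. After the visit come weekly and symptomatic EM use and two 72-hour Holters. The endpoint is binary at 12 months, so a recurrence that returns and is captured is only dated late. All of this stands. A reader might infer that the gap goes wholly unrecorded and that every failure in it becomes a success; the documents do not support that.

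A reader might also infer that first recurrences cluster in the gap. That fits Eff2 and Eff3, where about a third of post-blanking events fall in 14 of 270 days (5.2% of the time). It does not fit the default. Under Eff1 the Day 90–104 hazard is 0.00220 per day, below the 0.00316 and 0.00284 of the next two intervals.

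A third tempting inference is that sites, knowing the allocation, time the visit differently by arm. The documents show no such mechanism. The window is the same in both arms, randomization is stratified by site (9.2), and personnel doing follow-up evaluations stay blinded as far as possible (5.7). Unequal timing cannot be excluded, which is a reason to report it, but it is not shown.

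Finally, the Eff1 results with even visits lie inside the 0.0457 to 0.0543 band that SAP 14 accepts. That band describes simulation error and does not license a known bias, but it does show that the effect is small.

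**Conclusion.** The point holds in limited form, as a cheap improvement. As written, the plan can leave up to 13 full post-blanking days without protocol EM for subjects seen late in the window, and none for those seen by Day 90. The resulting bias runs towards non-inferiority. It is probably small: at most 0.5 percentage points of false non-inferiority under the default timing with even visits and up to half of gap failures never detected (5.2% against 4.7%). Under Eff2 and Eff3 with the same assumptions it reaches 7.2% and 6.3%. These figures rest on assumed visit timing and re-detection, a fixed sample size rather than the adaptive design, and the same undetected fraction in both arms. They do not show that the trial's type I error is materially out of control.

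**What to change.** In Protocol 4.7.6, 4.7.7 and 10.1.2, tie the start of monitoring to the calendar. At the Day 60 training, instruct each subject to begin weekly and symptomatic transmissions on Day 91, whatever the date of the Day 90 visit. Use that visit only to check compliance and retrain. State that the 80%-of-weeks rule in 10.1.2 is counted from Day 91, since its starting week is not given now. Report the day of first transmission by arm.

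The cost is wording in three sections and the training material, plus at most about two extra transmissions per subject for the core laboratory. Device delivery and training are already scheduled for Day 60, and the sample size plan need not change. Observed success may fall slightly in both arms, because failures now missed would be found.
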